All records will be kept strictly confidential as required by the policies and procedures of the University of Rochester where data are collected, processed, or reported. We plan to hold bi-weekly research meetings with the study team to provide monitoring to ensure subject safety as well as treatment integrity. The family can discontinue their participation at any time during the study.

Data Safety Monitoring Plan (DSMP):

This study also includes a Data Safety Monitoring Plan as submitted to and approved by the study sponsor: National Institutes of Health and National Heart, Lung, and Blood Institute. The plan for safety and monitoring is as follows:

- **Data and Safety Monitoring**

Data Quality Monitoring

The research associates will be responsible for all data collected during the assessments. They will receive training from key study personnel regarding asthma terminology, symptoms, medication understanding, and environmental assessment. They also will be trained by the project coordinator on the use of equipment for cotinine measurements and the NIOX VERO[®] instrument for collection of exhaled nitric oxide.

The project coordinators are all experienced in asthma terminology, symptoms and other aspects of the illness and have extensive training in research methods. They will oversee the data collection methods and all data will be reviewed by the study coordinators. Data forms will be completed at each study visit or telephone interview and will be returned with a cover sheet and other source documentation support materials (informed consent, contact information, etc.). Pre-intervention training of study staff will be conducted to increase knowledge about asthma, asthma medications, and other important information in order to reduce the number of “real-time” data collection errors. Through this training, staff will note any inconsistencies in parent reported data and will discuss them with the parent at the time of the interview.

Key study personnel will perform all follow-up interviews and follow-up data management. These data will be collected by the follow-up research associates who are independent from the research associate recruiters, and thus we will be able to perform blinded assessments of outcomes. Our team, including the principal investigator, senior project coordinator, and recruitment and follow-up project

coordinators, has a prior record of high-quality data collection and management. We have tracked hundreds of children in our randomized trials, and completed follow-ups with over 90% of subjects. Treatment group assignment will not be included with any follow-up materials in order to ensure blinding of the outcome assessment.

Once surveys have been administered, errors that can be corrected over the telephone (legibility, incorrect dates, etc.) will be done using telephone interviews. Simple range checks as well as cross-form validation checks will be performed to ensure the accuracy and completeness of the data. Any errors detected will be noted on the form (including initials and date of change). In addition, data forms, valid informed consent documents for each enrolled patient, and supporting source documentation materials will be reviewed by the research associates for accuracy. Required regulatory documents (IRB approval, updates to the protocol, data monitoring documents) will be maintained by the senior study coordinator. All events during the course of the trial including study enrollments, adverse events and study terminations will be reported to the senior study coordinator.

Safety Monitoring Plan

Potential risks related to participation in this study are minimal since the goal of this study is to ensure follow-up after an emergency visit and improve guideline-based asthma care for children with persistent asthma. In our prior school-based and office-based asthma programs, which have included hundreds of children, there have been no reports of significant adverse events related to study participation. The frequency and severity of all reported adverse events will be systematically recorded at each follow-up interview. Telephone interviewers will inquire about any adverse events, and specifically ask about hospitalizations, emergency visits and common side-effects from medications (yeast infections of the mouth, facial rash). Any significant adverse events will be flagged by the follow-up research associates and relayed promptly to the senior study coordinator, the principal investigator, the child's primary care provider, the Institutional Review Board, and the NIH. We will hold bi-weekly research review meetings with the study team to provide an additional layer of monitoring to ensure subject safety as well as treatment integrity. The NIH does not require a formal Data Safety Monitoring Board (DSMB) for this study

All records will be kept strictly confidential as required by the policies and procedures of the University of Rochester where data are collected, processed, or reported.

- **Potential Benefits**

Potential benefits for participants of the randomized trial exist for both groups of children (TEAM-ED and eUC). The goal is for children in the TEAM-ED group to have improved symptom assessment, adherence to preventive medications, and appropriate tailoring of therapy, thus they may experience less morbidity from asthma. Although children in the eUC group will not be receiving follow-up telemedicine assessments, we will prompt their PCP to provide guideline-based asthma care including prescription of the appropriate preventive medications and will provide regular reminders to PCPs and caregivers to care for the child's asthma. Improved asthma management should result in reduced morbidity for these children.

- **Analysis**

Sample Size:

Based on our experience with prior studies and the number of unique asthma visits to the ED, we expect to be able to enroll 430 child participants in 4 years. There are more than 950 individual patients -12 years of age with a primary diagnosis of asthma presenting to the 2 EDs each year, (450 at Strong Memorial, >500 at Rochester General), and >45% of these children live in the city of Rochester (>430).

Conservatively assuming enrollment of 1/4 of eligible subjects, we will have no difficulty enrolling 108 subjects/year. We anticipate a maximum of 15% attrition, based on an attrition rate of <5% in our prior studies. We therefore expect complete data on at least 365 children, randomized into 2 groups (182 subjects per group). We now consider power calculations based on this sample size.

The primary hypothesis is that children in TEAM-ED will have more symptom-free days at 3, 6, 9, and 12-months compared to eUC. Previous asthma interventions have demonstrated that improvements of 0.85-0.95 SFD/2 weeks are feasible and clinically meaningful.^{59,60} Based on our prior data, we estimate a pooled standard deviation (SD) of SFD to be 3.5 and within-subject correlation (ICC) of 0.3. We calculated power for the intervention effect on SFD while justifying repeated assessments for outcomes (3, 6, 9, 12 months).^{61,62} A sample size of 182 subjects per group will provide >90% power to detect a difference of 0.85 in SFD at a 2-sided 5% significance level.⁶³ We also calculated the smallest detectable differences in secondary outcomes with 80% power based on prior data.

We also aim to test whether children in TEAM-ED will have fewer unscheduled asthma visits over 12 months compared to eUC. Based on our preliminary data and data for similar populations, we estimate the baseline unscheduled asthma visit rate ranges 0.7-1.5 per person year. A sample size of 365 subjects will provide 80% power to detect a rate ratio of 0.7 if the control group has rate of 0.7 per person year. For preventive measures such as preventive medication use, in our prior study, 59% of children used a preventive medication at baseline. With 182 subjects in each group, we will have 90% power to detect an increase of 16% in using a two-sided Z test at a significance of 5%.

Primary Analysis:

Assess the effectiveness of TEAM-ED in reducing asthma morbidity and preventing repeat unscheduled asthma visits; Assess the effectiveness of the intervention in improving preventive asthma care. We will follow subjects prospectively throughout the year for clinical outcomes (symptoms, asthma control, health care use), functional outcomes (absenteeism, quality of life), and airway inflammation (FeNO). We will use graphs and descriptive statistics to summarize the primary and secondary outcomes by intervention group at each assessment point (baseline, 3, 6, 9 and 12 months). We will assess for differences between groups at baseline despite randomization in key characteristics (i.e.; age, race, ethnicity, insurance, caregiver education, caregiver depression, smoke exposure (determined by cotinine)). These comparisons will enable the identification of covariates to be controlled when evaluating the treatment effect. If distributional assumptions associated with a particular statistical procedure are violated, appropriate transformations will be made or non-parametric alternatives will be used. In accordance with the intention-to-treat principle,⁶⁴ all randomized subjects will be analyzed within the group to which they were assigned. Minimal crossover is expected. Hypothesis-driven comparisons will be made to control the family-wise type I error rate at 0.05 (two-sided) for the primary hypothesis.

For the primary outcome analysis, the time-course of treatment effect on SFD during the follow-up period will be evaluated using a linear mixed model (LMM) accounting for repeated measures within each subject to test the intervention effect of TEAM-ED over time, with SFD as the dependent variable, and intervention group and group by time interaction as independent variables.⁶⁵ The treatment effect will be regarded as fixed and the subjects as the random effect, with appropriate variance covariance structure specified. Interaction effects between intervention and follow-up period are included to catch possible differences in how SFD changes over time between intervention groups. Post treatment effects and maintenance gain from short to long term will be assessed by specifying appropriate linear contrasts. To adjust for potential confounding, baseline SFD and factors that differentiate between

groups will be included in the model as covariates. Model fitting statistics such as Information Criteria and difference in log likelihood will be used for model selection. Standard measures such as residual plots will check goodness-of-fit of the regression model assumptions and identify outliers. We will calculate intraclass coefficient (ICC) within providers; if autocorrelation is significant, provider will be included as another level of random effect in the mixed model to account for the nested data structure. If the outcome measure violates the normal assumption required by LMM, we will evaluate the intervention effect using Generalized Estimating Equations (GEE).⁶⁶ By specifying marginal mean effects of independent variables on the outcome variable, the GEE method offers consistent and robust estimates but does not require specification of a fully parametric distribution. Other continuous outcomes (quality of life, FeNO, absenteeism) will be analyzed similarly.

Categorical outcomes such as unscheduled asthma-related healthcare utilization will be analyzed by fitting Poisson regression models (with number of visits as the dependent variable). Estimation of the regression coefficients and standard errors will be obtained using the GEE method with a log link function and Poisson error. Baseline rate and factors imbalanced between groups will be controlled in this analysis. Other discrete outcomes (such as preventive medication use and availability of written asthma action plans) will be analyzed in a similar manner with appropriate link functions and response probability distributions specified.

The primary analyses will be performed according to the intention-to-treat principle and will include all randomized subjects. Substantial attention will be invested in participant retention; reasons for any subject withdrawals that may occur will be carefully documented. Missing data patterns will be examined by comparing subjects who discontinued with those who remained in the study. Inference based on the proposed methods GEE and/or LMM is valid provided that missing data follows the missing completely at random (MCAR) assumption. However, if the occurrence of missing data depends on the observed response but is independent of unobserved data (MAR), weight GEE (WGEE) will be used. Sensitivity analysis to the MAR assumption will also be carried out by modeling the between-group difference using WGEE.^{67,68} Separate secondary per protocol analyses will be performed, however, results of these analyses are potentially subject to bias and will be interpreted with appropriate caution.

Cost Effectiveness Analysis: *Establish the financial sustainability of the intervention with a specific focus on ultimate dissemination.* We will assess the health and economic benefits of TEAM-ED from both the societal and the Medicaid perspectives. We also will use Diffusion of Innovations Theory to help understand how this innovative model can be maintained in the current system of care.

We will use cost-effectiveness (CE) methodology^{69,70} to assess the health and economic benefits of TEAM-ED versus eUC over 12 months. The basecase analysis will be conducted from the societal perspective which includes all identifiable costs and benefits, regardless of whom they impact. Since the majority of subjects are eligible for Medicaid (73% based on prior work⁵⁹), a second analysis will take the Medicaid perspective. The intervention benefits will be assessed using the primary outcome (mean symptom-free days over 12 mos.).^{71,72}

Three main categories of costs to be considered include programmatic costs, productivity costs, and medical costs estimated at the individual child level. Programmatic costs include costs of initiating and running the program, hiring and training staff, purchasing or leasing equipment, staff travel, and information system costs. Programmatic costs will be tracked by the UR General Pediatric Division Administrator and the UR Telemedicine Program Administrator. Research-related costs that are not associated with the intervention and would not exist beyond the duration of the study will not be

included. Per person programmatic costs will be calculated by dividing the total costs of the program by the total number of children with persistent asthma in the EDs. We will determine productivity costs based on the amount of time parents take from work to care for sick children or take them to a doctor. Time from work will be valued at the median of the Bureau of Labor Statistics pay scale estimates based on age, race and gender. We will assess the impact of the intervention on medical costs using both parent-reported health care utilization data and medical record review. We will ask parents at each follow-up about their child's visits to the ED, urgent care facility, or primary care office, as well as hospitalizations. Health care use will be converted to costs using the NYS Medicaid fee schedule and other sources. Money spent out-of-pocket by caregivers to cover the cost of medical procedures, medications, or equipment will also be included in the medical costs. Annual medical costs per person will be analyzed using a 2-part model to adjust for zero expenses in a given year.⁷³ All costs will be adjusted to the last year of the intervention using the appropriate component of the Consumer Price Index (CPI).

We will consider the total cost of initiating and maintaining the program as well as the incremental cost-effectiveness ratio (ICER) of TEAM-ED versus eUC. The ICER is the difference in cost between the 2 study groups relative to the difference in the number of symptom-free days (SFD) gained between the 2 groups. The main outcome for the analysis from the societal perspective will be the ICER, defined as: $(\Delta Medical + \Delta Productivity + \$Program) / \Delta SFD$, where $\Delta = (TEAM-ED) - (eUC)$. We will bootstrap⁷⁴ the ICER to estimate standard error and to evaluate the uncertainty around the point estimate. The ICER will be compared to similar estimates from the literature.^{71,72} An acceptability curve, linking various values of 1 SFD to the probability of TEAM-ED being cost-effective, will be plotted.⁷⁵ The study from the Medicaid perspective will use the cost-benefit approach to economic evaluation. Benefits will be described as the net difference in medical and productivity costs between children in the TEAM-ED and eUC groups and accounts for a potential reduction in unplanned visits as well as an increase in number of preventive visits. The cost is equivalent to the cost of the program ($Net Monetary Benefit = \Delta Medical - \$Program$).

COVID-19

In response to the COVID-19 crisis, we will follow the Human Subjects Research guidelines outlined by the University of Rochester to continue enrollment for this study. Please find the following link for these guidelines: <https://www.urmc.rochester.edu/coronavirus/coronavirus-research/guidance-for-researchers/human-subjects-research.aspx>. We will minimize in-person contacts to only those tasks necessary to conduct the research (e.g., obtaining consent, collecting breathing measurements if needed). We will ensure that team members are appropriately trained in safety measures, maintain social distancing when possible, use personal protective equipment for themselves and research subjects (and family members), and will ensure proper cleaning/sanitizing of hands, equipment and workstations. We will continue to monitor and follow the updated guidelines put forth by the UofR in the link above.

We've included a brief, optional survey to assess how the COVID-19 Crisis is affecting children with asthma and their families. We will ask the caregivers if they would be willing to answer these questions at the end of follow-up surveys that we are already conducting.

References

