This is a randomized trial of the TEAM-ED intervention versus an enhanced usual care (eUC) comparison group with 430 urban children (and their caregivers) aged 3-12 who present to the emergency department for an asthma exacerbation. Children presenting to the ED will be systematically screened, and eligible children will be randomly assigned to either the TEAM-ED intervention (telemedicine asthma assessment and follow-up visits using a pre-developed template with guideline-based prompting) or the eUC comparison condition (asthma screening with symptom reports and guideline-based recommendations for preventive medications sent to the PCP, and systematic feedback to the PCP and caregiver to promote appropriate follow-up care). Randomization will be stratified by enrollment site and use of a preventive asthma medication at baseline. A permuted block design will be used to assure an equal balance of children in each group over time. Following randomization, children will be followed prospectively and systematically for a year.

Subjects and Setting:

There are 2 EDs (Strong Memorial Hospital (SMH), Rochester General Hospital (RGH)) that provide pediatric emergency care for children in Rochester and the surrounding areas. Children 4-12 years of age presenting to the ED at either site will be screened for eligibility. A total of 430 children and 430 caregivers will be recruited into the study over 4 consecutive years.

Inclusion Criteria (all 4 criteria must be met):

- Prior doctor report stating that the child has asthma or reactive airway disease (RAD).
- Current emergency visit for an acute asthma exacerbation.
- Age ≥ 3 and ≤ 12 years, and living in the city of Rochester (primary residence within the following zip codes: 14428, 14445, 14467, 14513, 14514, 14515, 14586, 14604, 14605, 14606, 14607, 14608, 14609, 14610, 14611, 14612, 14613, 14614, 14615, 14616, 14617, 14618, 14619, 14620, 14621, 14622, 14623, 14624, 14625, 14626).
- Persistent asthma or poor asthma control, defined by NHLBI guidelines⁴⁰ as any 1 of the following:
 - >2 days/wk with asthma symptoms in the past month,
 - >2 days/wk with rescue medication use in the past month,
 - >2 days/month with nighttime symptoms in the past month or
 - ≥ 2 episodes of asthma during past year that required systemic corticosteroids (including the current emergency visit).

Exclusion Criteria:

- Inability to speak and understand either English or Spanish.

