Participants will be given the option to allow for future contact for other research studies at the time of consent. All participants who provided permission will be added to a future contact database dedicated to childhood asthma research (RSRB #31010). A voluntary photo/image consent form will be signed at the 12 month final home visit and images will be used only for study related purpose of publications, conferences, handouts, pamphlets, and presentations/posters.

- **Randomization**

Following completion of the baseline assessment in the ED, each child will be randomly assigned to either the TEAM-ED or eUC group. Randomization will be stratified by enrollment site and use of a preventive asthma medication at baseline. A permuted block design will be used to assure an equal balance of children in each group over time. The randomization scheme will be independently developed by the Biostatistics Center, and will be implemented electronically via REDCap™.

- **TEAM-ED Group:**

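### The symptom-free-day and visit-count models name neither randomization stratification factor, so the reported standard error may be slightly too wide

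*Combined protocol and SAP*

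**What the plan says.** The Randomization section states: "Randomization will be stratified by enrollment site and use of a preventive asthma medication at baseline". Study Design gives the same strata and adds: "A permuted block design will be used to assure an equal balance of children in each group over time".

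Under Analysis, Primary Analysis, the SFD mixed model has "intervention group and group by time interaction as independent variables". Covariates come next: "To adjust for potential confounding, baseline SFD and factors that differentiate between" the groups. The comparison that identifies those factors covers "key characteristics (i.e.; age, race, ethnicity, insurance, caregiver education, caregiver depression, smoke exposure (determined by cotinine"), and its purpose is explicit: "These comparisons will enable the identification of covariates to be controlled when evaluating the treatment effect". No criterion is given for when a factor counts as differing.

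The visit-count model (Poisson, log link, GEE) follows the same pattern: "Baseline rate and factors imbalanced between groups will be controlled in this analysis". Other discrete outcomes are to be handled in the same way with suitable link functions.

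Two further steps could change the SFD model. One is "Model fitting statistics such as Information Criteria and difference in log likelihood will be used for model selection". The other is a provider random effect, added if within-provider correlation is significant. Neither mentions the strata.

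**The concern.** Stratified blocks remove the strata from the true sampling variability of the treatment comparison. A model without the strata leaves their variance in its residual and so reports more uncertainty than the design produces. The analysis then does not match the randomization.

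The plan's rule for adding covariates does not repair this. It admits factors that are imbalanced, and stratification prevents imbalance in exactly these two. It also leaves the covariate set of the primary model open until group-level baseline data have been seen.

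At stake is some precision: a confidence interval a little too wide and a test a little conservative. Validity is not at stake.

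**Working it through.** **Inputs from the plan (Sample Size).** SD of SFD 3.5, within-child correlation 0.3, four follow-ups, 182 per group, difference 0.85 SFD, two-sided 5%; 59% used a preventive medication at baseline in a prior study; control visit rate 0.7 per person-year.

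**Assumptions.** Correlation of baseline SFD with each follow-up, 0.3. R2, the share of the residual variance of a child's time-averaged SFD (after baseline SFD) that the strata explain: 0, 2, 5 or 10%. Block sizes 4 to 8.

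**1. The plan's own power.** Variance of the four-visit average = 12.25 × (1 + 3 × 0.3)/4 = 5.819, so SD 2.412 and SE = 2.412 × √(2/182) = 0.253. Power = Φ(0.85/0.253 − 1.96) = 91.9%, which agrees with the stated figure above 90%. A single visit gives 63.9%, so the stated power refers to the time-averaged difference.

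**2. Could the imbalance rule admit the strata?** With block size b, each of the two strata that form one level of a factor can have an excess of at most b/2 in one arm. The largest gap is b/215 with 215 randomized per arm: 4/215 = 1.9 to 8/215 = 3.7 percentage points. The rule is unlikely to pick them up even if they were on the comparison list.

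**3. Effect on the SE.** Baseline adjustment gives variance 5.819 − 0.3² × 12.25 = 4.716 and reported SE √(2 × 4.716/182) = 0.228. The true SE is 0.228 × √(1 − R2). Hence:

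- overstatement = 1/√(1 − R2) − 1
- type I error = 2 × [1 − Φ(1.96/√(1 − R2))]
- power without strata = Φ((0.85 − 1.96 × 0.228)/(0.228√(1 − R2)))
- power with strata = Φ(0.85/(0.228√(1 − R2)) − 1.96)

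| R2 | SE overstated | Type I error | Power without strata | Power with strata |
|---|---|---|---|---|
| 0% | 0% | 5.0% | 96.2% | 96.2% |
| 2% | 1.0% | 4.8% | 96.3% | 96.5% |
| 5% | 2.6% | 4.4% | 96.6% | 96.9% |
| 10% | 5.4% | 3.9% | 96.9% | 97.6% |

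**4. What those R2 values require.** If medication use alone carries the effect, the user versus non-user gap after baseline adjustment is √(R2 × 4.716/(0.59 × 0.41)), which is 0.62, 0.99 and 1.40 SFD for 2, 5 and 10%. A gap of 0.85 SFD gives R2 3.7%, SE overstated by 1.9% and type I error 4.6%.

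**5. Other SFD quantities.** At a single visit the residual variance is 12.25 × (1 − 0.09) = 11.148, so the same strata variance is an R2 of 0.85, 2.12 and 4.23%. The SE is overstated by 0.4, 1.1 and 2.2%, and type I error is 4.9, 4.8 and 4.5%. For the 12-minus-3-month contrast there is no effect if the strata effects are constant over time.

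**6. Simulation.** 20,000 null trials per setting, 364 children, blocks of 4 in four strata, sites split 50:50 (assumed), strata variance shared equally between the two factors, baseline SFD in both models. Type I error without / with the strata (Monte Carlo SE about 0.15 points):

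| R2 | Time average | 12-month visit | 12 minus 3 months | Joint 4-df test |
|---|---|---|---|---|
| 0% | 4.7 / 4.7 | 5.0 / 5.0 | 4.9 / 4.8 | 4.9 / 4.9 |
| 2% | 4.6 / 4.8 | 4.8 / 5.0 | 5.0 / 5.0 | 4.8 / 4.8 |
| 5% | 4.5 / 4.9 | 4.7 / 4.9 | 5.2 / 5.2 | 4.7 / 5.0 |
| 10% | 3.8 / 4.9 | 4.6 / 5.1 | 5.3 / 5.2 | 4.6 / 5.0 |

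In a separate run of 4,000 trials at R2 10%, the ratio of reported SE to the empirical SD, strata omitted, was 1.055 under stratified and 1.00 under unstratified randomization. The excess therefore comes from stratifying and then omitting the factors.

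**7. Visit counts.** Assume a rate ratio RR between medication strata after adjustment for the baseline rate. With m = 0.7/(0.59 + 0.41 × RR), the between-strata variance is v = 0.59 × 0.41 × (m(RR − 1))², and R2 = v/(0.7 + v). RR 1.5 and 2.0 give R2 2.8 and 7.9%, so the robust SE is overstated by 1.4 and 4.2% (0.8 and 2.4% with added overdispersion of 1). In 6,000 null trials, type I error without / with strata was 4.8 / 5.1% and 4.0 / 4.9%.

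**The case against.** **The effect is small, conservative and assumed.** This stands. The power given up is 0.2, 0.3 and 0.7 points at R2 of 2, 5 and 10%. The top value needs a medication gap about 1.6 times the 0.85 SFD the trial is powered for, and at R2 of 0 nothing is lost.

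**Attrition loosens the balance.** Blocks balance the children randomized, whereas 182 per group is the number left after 15% attrition. If all 15% are lost at random with no follow-up data, about 16% of the strata variance returns to the estimate, and the overstatement becomes 0.9, 2.2 and 4.5%. This is right. It lowers the top of an assumed range and leaves the direction unchanged. The balance bound is unaffected, because the plan compares groups at baseline.

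**The time average is the most affected quantity.** The plan also describes effects at each visit and contrasts over time, where the effect is smaller or nil. True, but the stated power rests on the time average.

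**Model selection might bring the strata in.** If they were candidates, the likelihood-ratio statistic with 364 children would be about −364 × ln(1 − R2): 19 at 5% and 38 at 10%, on 2 df. They would then be kept where they matter most. The plan does not make them candidates, and provider is not enrollment site.

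**Imbalance-driven covariate choice is a separate matter.** In part it is, and none of these figures measure it. The same sentence of the plan is the source of both.

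**Conclusion.** The omission is clear on the text. Its consequence is a reported SE for the time-averaged SFD difference that is too wide by 0 to 5.4% over an assumed R2 of 0 to 10%, or up to about 4.5% if the full 15% attrition leaves no data. A medication gap as large as the design difference would give about 2%.

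The range depends on how R2 is defined. Read instead as a share of single-visit variance, 10% would mean 12.5% (14.4% after baseline adjustment). That would need a medication gap of √(0.10 × 11.148/(0.59 × 0.41)) = 2.15 SFD.

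The estimate is not biased, false positives are not inflated, and power above 90% stands. For the preventive-medication outcome, the analogous-methods wording plausibly brings in baseline use, so only site would be missing there. This is a worthwhile and nearly free improvement, not a threat to the trial's conclusion.

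**What to change.** - In the SFD model, include enrollment site and baseline preventive medication use as fixed covariates alongside baseline SFD. Do the same in the visit-count model alongside the baseline visit rate, and in the other outcome models.
- For outcomes with a logit link, state that the odds ratio is then conditional on the strata.
- Name any further covariates on prognostic grounds before group-level data are seen.
- Keep the baseline comparisons as description, or use imbalance-based adjustment only as a sensitivity analysis.

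The cost is wording in the analysis plan and about two degrees of freedom. Both variables are already collected for randomization.

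### Apart from the baseline value of the outcome, covariates are chosen by observed baseline imbalance on an undefined criterion, when a short prognostic set could be fixed in advance

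*Combined protocol and SAP*

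**What the plan says.** In the combined protocol and SAP, under Analysis, Primary Analysis, the plan states: "We will assess for differences between groups at baseline despite randomization in key characteristics". It names seven: age, race, ethnicity, insurance, the caregiver's education and depression, and smoke exposure by cotinine. It then gives the purpose: "These comparisons will enable the identification of covariates to be controlled when evaluating the treatment effect".

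The rule is carried into both main models.

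- SFD mixed model: "To adjust for potential confounding, baseline SFD and factors that differentiate between" "groups will be included in the model as covariates" (one sentence, split by a page break).
- Poisson model for visits: "Baseline rate and factors imbalanced between groups will be controlled in this analysis".

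Each model therefore has one unconditional covariate, the baseline value of the outcome. All others are conditional on imbalance. The plan gives no test, threshold or metric for imbalance.

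The Randomization section says: "Randomization will be stratified by enrollment site and use of a preventive asthma medication at baseline". Neither stratification factor is named as a covariate in either model.

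**The concern.** Allocation is by permuted blocks, prepared independently and run electronically. A baseline difference between the arms is then a chance event and not a sign of confounding. Whether a factor happens to differ says nothing about whether it predicts SFD. A strong predictor that is balanced is left out, and a weak one that differs by chance is let in.

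Two things are at stake. First, the primary model is not fixed until the baseline data have been compared, and with no stated criterion it could be settled after outcomes are known. Second, the trial collects baseline measures that could sharpen the treatment estimate, and a rule that seldom uses them gives up that precision.

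The stratification factors are a related gap. Because they are balanced by design, an imbalance rule would seldom select them.

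**Working it through.** **Inputs from the documents (Analysis, Sample Size).** 182 children per group; difference 0.85 SFD per two weeks; two-sided 5%; four follow-ups (3, 6, 9 and 12 months); and "we estimate a pooled standard deviation (SD) of SFD to be 3.5 and within-subject correlation (ICC) of 0.3".

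**Step 1: reproduce the plan's power.** The claim is: "A sample size of 182 subjects per group will provide >90% power to detect a difference of 0.85 in SFD at a 2-sided 5% significance". For a time-averaged difference:

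- Variance factor V = (1 + 3 × 0.3)/4 = 0.475.
- SD of the four-visit mean = 3.5 × √0.475 = 2.412.
- SE = 2.412 × √(2/182) = 0.253.
- Power = Φ(0.85/0.253 − 1.96) = 91.9%.

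The figure reproduces with no covariates, so the sample size does not rest on the covariate rule.

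**Step 2: add baseline SFD, which the plan always includes.** The documents give no correlation between baseline and follow-up. I assume 0.3, extending the plan's ICC to baseline.

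- Variance explained = 0.3²/0.475 = 0.19.
- Residual SD = 3.5 × √(0.475 − 0.09) = 2.172.
- SE = 2.172 × √(2/182) = 0.228; power = 96.2%.

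This is the right starting point for judging the rule.

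**Step 3: how often the rule selects something.** For seven independent characteristics (an assumption; several are probably correlated), the chance that at least one is flagged under correct randomization is 1 − (1 − p)^7:

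| Reading of imbalance | Chance of at least one |
|---|---|
| p<0.05 | 30% |
| p<0.10 | 52% |
| p<0.20 | 79% |
| standardized difference >0.1 | about 95% |

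**Step 4: precision, rule against fixed set.** The documents do not say how much the seven explain beyond baseline SFD, so I use an assumed range. Closed form, SE = 0.228 × √(1 − extra R²): 0.222, 0.216 and 0.204 for 5%, 10% and 20%, with power 96.9%, 97.6% and 98.7%.

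Simulation (8,000 trials per setting, seven covariates of equal strength, selection at p<0.05, baseline SFD always in the model) also allows for estimating seven coefficients:

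| Extra R² | SE, rule | SE, all seven | Power, rule | Power, all seven | Type I error, rule |
|---|---|---|---|---|---|
| 5% | 0.228 | 0.224 | 96.0% | 96.5% | 4.6% |
| 10% | 0.228 | 0.218 | 96.5% | 97.6% | 4.5% |
| 20% | 0.227 | 0.206 | 96.4% | 98.5% | 4.2% |

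With baseline SFD alone the SE is 0.228 throughout, so the rule recovers almost none of the available precision. The power gain here is about 0.6, 1.1 and 2.1 points. A second set of simulated trials gave 0.5 to 1.6. The two sets differ by simulation error, so I take the gain as roughly 0.5 to 2 points.

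**Step 5: how much the undefined criterion matters.** Apply the four readings in Step 3 to the same simulated trials. At an assumed true effect of 0.5 SFD, they do not all agree on significance in about 6%, 10% and 14% of trials (extra R² 5%, 10%, 20%). At 0.85 SFD the figure is about 2%.

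**Visit model.** The documents give no association between any covariate and visit counts, so no gain can be computed.

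**The case against.** The strongest defence is that the plan already makes the adjustment likely to matter most. The baseline outcome enters both models unconditionally, and under the Step 2 assumption it alone lifts power from 91.9% to 96.2%. The candidate characteristics are named in advance, which limits discretion. Type I error under a p<0.05 rule is at or slightly below 5%. All R² values are assumptions. This stands, and it is why the point is minor.

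Three stronger readings are tempting, and the documents do not support them.

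- A reader might infer that no covariate enters unless the arms differ. The sentences on both models contradict that for baseline SFD and the baseline visit rate.
- A reader might infer that selecting on imbalance inflates type I error or undercuts the sample size. The simulation shows no inflation, and the stated power holds without adjustment.
- A reader might measure the gain from the sample-size variance (SE 0.253, power about 92%) and credit it all to the extra covariates. That omits baseline SFD, which under the assumed correlation already brings the SE to 0.228.

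The defence does not answer the selection rule itself. Naming candidates does not fix the model when the criterion for entry is unstated, and chance imbalance remains a poor guide to prognosis.

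**Conclusion.** The point holds as a cheap improvement of minor severity. Beyond the baseline outcome value, the plan lets chance imbalance, on an unstated criterion, decide which covariates enter the SFD and visit models. The primary model is therefore not fully fixed in advance, and nearly all the precision available from the other baseline measures is forgone.

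For SFD, the SE could be about 2%, 4% or 9.5% narrower at the three assumed R² values. These sizes rest on the assumed baseline correlation of 0.3, the assumed R² range, independent covariates of equal strength, and a p<0.05 reading of the rule. The main gain is one fixed model, whatever the imbalance turns out to be.

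**What to change.** Remove baseline comparison as the route to covariates, and present the baseline table descriptively, without tests. In the SAP, before unblinding, fix one set for the SFD and visit models:

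- the baseline value of the outcome, as now;
- both stratification factors, enrollment site and baseline preventive medication use;
- a short prognostic list from the characteristics already named, for example age, insurance, caregiver education, CES-D score and log cotinine.

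The documents do not show which of these predict SFD best, so the investigators should settle the list from their prior data or clinical judgement, without reference to this trial's outcomes. Include the set whether or not the arms differ, and state a simple imputation for missing baseline covariates so that no child is dropped.

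The cost is SAP wording and a few degrees of freedom out of about 365 children. The listed variables are all collected at baseline according to the Measures table and the randomization procedure, so no new data are needed.
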